17.2. Retention of Records

The principal investigator must maintain all documentation relating to the study for the period outlined in the site contract, or for a period of 2 years after the last marketing application approval, and until there are no pending or contemplated marketing applications in an ICH region or at least 2 years have elapsed since the formal discontinuation of clinical development of the IP. Sage is responsible to inform the investigator/institution as to when study documents no longer need to be retained.

18. PUBLICATION POLICY

All information concerning SAGE-324 is considered confidential and shall remain the sole property of Sage Therapeutics. The investigator agrees to use this information only in conducting the study and shall not use it for any other purposes without written approval from Sage Therapeutics. No publication or disclosure of study results will be permitted except as specified in a separate, written, agreement between Sage Therapeutics and the investigator.

Protocol Amendment 5 reflects the following changes:

• The Sponsor Contact has changed from:

• The Sponsor Medical Monitor and Study Physician have changed from:

- Section 9.2.2 Prohibited Medications: As per Administrative Letter #7 dated July 17, 2023, the following was added for clarity:
 - Any estrogen-containing products that are widely absorbed into the systemic circulation (eg, oral, transdermal, transvaginal, etc.), used for any indication, are prohibited from Day -14 and during the study.
- Section 2 Synopsis, Section 7.1 Overall Study Design, and Section 9.2.3 Other Restrictions:
 - Updated guidance regarding gaining experience with how the study drug may affect the participant before engaging in potentially hazardous activities requiring mental alertness, such as driving.

324-ETD-202 Protocol Summary of Changes Version 6.0, Amendment 5

- Section 12.4 Overdose was changed to Section 12.4 Special Considerations, with new language for "abuse" and "misuse" to align with the Regulation (EU) No 536/2014 Of the European Parliament and Of The Council.
- Section 13.1 Data Analysis Sets and Section 2.2 Synopsis, the definition of the Full Analysis Set was updated to include participants enrolled under Version 1 of the protocol (dated 03 September 2021), who previously participated in a SAGE-324 study.
- The Sponsor Approval page was deleted to align with current Sage process and template.
- Minor formatting changes

Date of Amendment: 10 January 2023

A PHASE 2, DOUBLE-BLIND, RANDOMIZED, PLACEBO-CONTROLLED, DOSE-RESPONSE STUDY OF SAGE-324 FOR THE TREATMENT OF ESSENTIAL TREMOR

Rationale for Protocol Amendment

The purpose for this protocol amendment is to update eligibility criteria and statistical analyses to include participants who are receiving propranolol for the treatment of essential tremor (ET).

Changes to the protocol include:

- Update objectives and endpoints to include monotherapy cohort (SAGE-324), adjunct therapy cohort (SAGE-324 + propranolol), and overall population (Synopsis and Section 6)
- Update sample size, stratification, and other statistical analyses to include monotherapy cohort and adjunct therapy cohort (Synopsis, Schedule of Assessments footnotes, Section 7.1, Section 7.2, Section 7.3, Section 8.4.4, Section 9.5, Section 13.4, Section 13.5, Section 13.6, and Section 13.8)
- Include additional 14 days (total of 42 days) in the Screening Period for sufficient time to taper ET medications other than propranolol after approval from the sponsor (Synopsis, Figure 1, and Section 7.1)
- Include information that participants in the adjunct therapy cohort must be on stable dose of propranolol (maximum total daily propranolol dose up to 320 mg allowed) for the treatment of ET from 3 months prior to screening through Day 90 of the study and that no additional propranolol as needed (PRN) is allowed (Inclusion criterion 8 [Synopsis and Section 8.1] and Section 9.2.2.1)
- Clarify that, a participant is to be excluded if receiving propranolol treatment for a medical condition other than ET (Exclusion criterion 9 [Synopsis and Section 8.2] and Section 9.2.2.1)
- Correction to the volume of distilled spirits (Inclusion criterion 9 [Synopsis and Section 8.1] and Section 9.2.3.
- Prohibit use of Cala Trio bracelet for treatment of ET from 2 weeks prior to Day 1 through Day 97 (Exclusion criterion 4 [Synopsis and Section 8.2] and Section 9.2.3)
- Clarify that prohibited use of botulinum toxin is for treatment of ET (Exclusion criterion 5 [Synopsis and Section 8.2])
- Include statement that there is currently no evidence of drug-drug interactions for SAGE-324 except for those outlined in the inclusion/exclusion criteria (Section 5.2)
- Clarify process for participant enrollment in a SAGE-324 long-term open label study (Synopsis, Section 7.1, and Section 9.3)

324-ETD-202 Protocol Summary of Changes Version 5.0, Amendment 4

• Include nicotine products and alcohol use as part of medical history and monitoring during the study (Schedule of Assessments and Section 12.1.1)

Updates to organization, formatting, terminology, and Sage personnel have also been made.

Date of Amendment: 04 May 2022

A PHASE 2, DOUBLE-BLIND, RANDOMIZED, PLACEBO-CONTROLLED, DOSE-RESPONSE STUDY OF SAGE-324 FOR THE TREATMENT OF ESSENTIAL TREMOR

Rationale for Protocol Amendment

The main purpose for this protocol amendment is to update eligibility criteria.

Changes to the protocol include:

- Permit alcohol consumption with restrictions on amount and timing with scheduled study visits (Inclusion Criterion 9 [Synopsis and Section 8.1] and Section 9.2.3)
- Permit current use of nicotine products at prestudy levels (new Inclusion Criterion 13 [Synopsis and Section 8.1] and Section 9.2.3)
- Exclude participants with nicotine use disorder (Exclusion Criterion 11 [Synopsis and Section 8.2] and Section 9.2.3)
- Remove alcohol and cotinine screening (Table 2 Schedule of Assessments and Section 12.1.6.1)
- Clarify that use of tremorgenic drug is prohibited within 14 days or 5 half-lives (whichever is longer) prior to Day 1 and that the use of established treatments with tremorgenic drugs is permitted if they do not cause or exacerbate tremors (Exclusion Criterion 2 and Section 9.2.2)
- Include creatine kinase, myoglobin, and HgA1c in clinical laboratory assessments (Table 2 and Section 12.1.6)
- Clarify that participants should not engage in potentially hazardous activities requiring mental activities until any sleepiness and sedative effects of IP have dissipated (Synopsis and Section 7.1)
- Prohibit use of estrogen-containing contraceptives that are widely absorbed into the circulatory system as an acceptable forms of highly effective contraception methods for participants of childbearing potential or for partners of male participants who are of childbearing potential (Section 9.2.4)
- Update safety reporting requirements (Table 1, Section 12.2.4, Section 12.2.6, Section 12.3, and Section 12.4)

Updates to organization, formatting, descriptions of procedures, and Sage personnel have also been made.

Date of Amendment: 04 May 2022

A PHASE 2, DOUBLE-BLIND, RANDOMIZED, PLACEBO-CONTROLLED, DOSE-RESPONSE STUDY OF SAGE-324 FOR THE TREATMENT OF ESSENTIAL TREMOR

Rationale for Protocol Amendment

The main purpose for this protocol amendment is to remove protocol.

from the

Additional changes to the protocol include:

- Update end of study information to include the opportunity to participate in a SAGE-324 long-term open-label safety study
- Clarify in exclusion criterion 12 that participants will not have known allergy to SAGE-324 because the study does not currently allow participants to have prior exposure to SAGE-324
- Clarify that prior essential tremor medications may be restarted following Day 97 of the study
- Harmonize treatment groups to include placebo throughout document

Updates to organization, formatting, and Sage personnel have also been made.

Date of Amendment: 04 March 2022

A PHASE 2, DOUBLE-BLIND, RANDOMIZED, PLACEBO-CONTROLLED, DOSE-RESPONSE STUDY OF SAGE-324 FOR THE TREATMENT OF ESSENTIAL TREMOR

Rationale for Protocol Amendment

The purpose for this protocol amendment is to update and clarify the protocol regarding the following:

- Clarify eligibility requirements with minor textual changes to inclusion criteria 3, 6, and 7 and exclusion criteria 1, 6, and 11 and addition of a new exclusion criterion 25
- Update Table 2 Schedule of Assessments as follows:
 - In table: update dispensing of IP to include Day 71 Visit
 - Footnote (d) for ECGs: delete triplicate sampling to harmonize with Section 12.1.5

_	Footnote (h): split footnote g in original version into new footnotes g and h to

- Footnote (h): split footnote g in original version into new footnotes g and h to clarify importance of washout of prestudy essential tremor drugs prior to first TETRAS assessment

- Clarify importance of prestudy essential tremor medication washout in Section 9.2.2 by addition of subsection header before existing text (new Section 9.2.2.1)
- Update end of study activities to include an offer to all participants for enrollment to a SAGE-324 long-term open-label study (Section 9.3)
- Update descriptions of efficacy assessments
- Update ECG assessment from triplicate to single readings at all timepoints (Section 12.1.5)
- Clarify procedures and assessments throughout the protocol with minor textual changes
- Update personnel for Sponsor Contact and Sponsor Medical Monitor/Study Sage
 Physician

324-ETD-202 Protocol Summary of Changes Version 2.0, Amendment 1

A new section (Section 12.2.4) describing reporting procedures for Urgent Safety Measures and Unanticipated Problems has been added in response to regulatory feedback.

Updates and corrections to organization, terminology, punctuation, grammar, abbreviations, and formatting have also been made.

1. LIST OF ABBREVIATIONS

The following abbreviations and specialist terms are used in this statistical analysis plan (SAP).

Abbreviation	Definition		
AE	adverse event		
ADL	activities of daily living		
AR(1)	Autoregressive (1)		
ATC	Anatomical Therapeutic Chemical		
BMI	body mass index		
ECG	electrocardiogram		
eCRF	electronic case report form		
EOS	End-of-Study		
EOT	End of Treatment		
ET	essential tremor		
ETV	Early Termination Visit		
IP	investigational product		
MedDRA	Medical Dictionary for Regulatory Activities		
MMRM	Mixed Effects Model for Repeated Measures		
PCS	potentially clinically significant		
PCSC	potentially clinically significant change		
PT	Preferred Term		

Table 1: **Abbreviations and Specialist Terms**

Abbreviation	Definition	
QTcF	QT corrected according to Fridericia's formula	
SAE	serious adverse event	
SAP	statistical analysis plan	
SD	standard deviation	
SOC	System Organ Class	
TEAE	treatment-emergent adverse event	
TETRAS	The Essential Tremor Rating Assessment Scale	
WHO-DD	World Health Organization Drug Dictionary	

2. INTRODUCTION

This SAP is for the final analysis of clinical study protocol SAGE-324-ETD-202 and is based on the approved clinical study protocol, dated on 02 November 2023, Version 6.0.

This SAP addresses the objectives of the study and describes the planned statistical analyses and data presentations. All analyses and data presentations will be generated using SAS[®] Version 9.4 or higher software (SAS Institute, Cary, North Carolina, USA). This SAP will be finalized and approved before the clinical database lock. Any changes made to the SAP after the clinical database lock has occurred will be documented and discussed in the clinical study report for this study.

3. **STUDY OBJECTIVES**

Primary Objective 3.1.

The primary objective of this study is to evaluate the dose-response relationship of different doses of SAGE-324 on upper extremity tremor in the monotherapy cohort.

3.2. **Secondary Objectives**

The secondary objective of this study is to evaluate the dose-response relationship of different doses of SAGE-324 on specified activities of daily living (ADL) in the monotherapy cohort.

4. STUDY ENDPOINTS

4.1. Efficacy Endpoint

4.1.1. Primary Efficacy Endpoint

The primary efficacy endpoint of this study is the change from baseline in TETRAS Performance Subscale Item 4 (upper limb) total score on Day 91 in the monotherapy cohort.

4.1.2. Secondary Efficacy Endpoint

The secondary efficacy endpoint of this study is the change from baseline in TETRAS ADL composite score in the monotherapy cohort.

4.1.3. Primary and Secondary Efficacy Endpoint Estimand

The estimand for the primary and secondary efficacy endpoint is defined as follows:

- There are 4 treatment groups for the monotherapy participants to be evaluated: SAGE-324 (15 mg, 30 mg, 60 mg) and placebo.
- The target population consists of the monotherapy participants ages 18 to 80 years and have a diagnosis of ET with combined total upper limb TETRAS Performance Subscale Item 4 of at least 12 with the dominant upper limb score of at least 6 and baseline TETRAS ADL score of at least 20.
- The outcome for the primary efficacy endpoint is the change from baseline in TETRAS Performance Subscale Item 4 score on Day 91 in the monotherapy cohort.
- The population-level summary measure is the dose-response of different doses of SAGE-324 and placebo for the monotherapy cohort.
- The treatment/hypothetical policy strategy will be adopted for the primary and secondary endpoint. For data collected after the intercurrent events, such as rescue medication, the treatment policy strategy will be used. For data not available after the intercurrent events, like premature discontinuation of study treatment, the hypothetical policy strategy will be adopted. This means that the dose-responses of different dose groups will be analyzed using all observed on-study data, using appropriate visit mapping specified in Table 2, regardless of the occurrence of the intercurrent event, including use of additional medication, premature discontinuation of treatment for any reason, or other protocol violations.

Statistical Analysis Plan Methods Version 1.0 17-Jun-2024 Protocol Number: 324-ETD-202 (Version 6.0 2 November 2023)

4.2. Safety Endpoints

The safety endpoints of this study are:

- Incidence of treatment-emergent adverse events (TEAEs)
- Change from baseline in vital signs
- Change from baseline in electrocardiogram (ECG) parameters
- Change from baseline in clinical laboratory parameters (eg, serum chemistry, hematology, coagulation, and urinalysis)

5. STUDY DESIGN

5.1. Overall Design

This study is a Phase 2, randomized, double-blind, placebo-controlled, dose-ranging study to evaluate the efficacy, safety, and tolerability of SAGE-324 in participants with ET. Participants, site staff, and sponsor personnel will be blinded to treatment allocations. This study includes a Screening Period of up to 28 days, a 90-day double-blind Treatment Period (90 days of dosing), and a 14-day Follow-up Period. See the Schedule of Assessments (Appendix A) for the full list of study assessments and timings. A schematic of the study is presented in Figure 1.

Participants who have provided informed consent will undergo screening assessments to determine eligibility. The Screening Period may be extended for an additional 14 days (to a total of 42 days) for subjects requiring additional time to taper ET medication (other than propranolol), after approval from the sponsor.

Following completion of screening and Day 1 eligibility assessments, participants will be randomly assigned to 1 of 4 treatment groups (placebo or SAGE-324: 15 mg, 30 mg, or 60 mg, oral daily) in a 1:1:1:1 ratio, stratified by baseline propranolol use (adjunct therapy).

The 15-mg dose group will receive 15 mg of SAGE-324 from Day 1 to Day 90.

The 30-mg dose group will receive 30 mg of SAGE-324 from Day 1 to Day 90.

The 60-mg dose group will receive 15 mg of SAGE-324 from Day 1 to Day 14, then 30 mg from Day 15 to Day 28, then 45 mg from Day 29 to Day 42, and then 60 mg from Day 43 to Day 90.

Starting on Day 1, after randomization, participants will receive a single dose of IP once daily for 90 days on an outpatient basis, to be taken before bed, with a snack if bedtime is not within 2 hours of the evening meal. During the Treatment Period, participants will return to the study center for efficacy and safety assessments as specified in Appendix A.

Follow-up visits will be conducted on an outpatient basis on Days 97 and 104. Participants will continue to complete questionnaires as indicated in Appendix A and will return to the clinic approximately 6 days after the last dose of IP (ie, Day 97) for efficacy and safety monitoring. Participants will return to the study center for an End of Study (EOS) visit approximately 13 days following the last dose of IP (ie, Day 104); the EOS visit will be conducted at the time of discontinuation if this occurs any time before Day 104.

No dose reductions of SAGE-324 will be permitted.

Figure 1: Study Design

Abbreviation: R = TETRAS = The Essential Tremor Rating Assessment Scale Note: The Screening Period may be extended for an additional 14 days (total of 42 days) for subjects requiring additional time to taper ET medication (other than propranolol), after approval from the sponsor.

5.2. Sample Size and Power

The planned sample size is 160 participants, randomized in a 1:1:1:1 ratio to each of the dose groups (placebo and SAGE-324: 15 mg, 30 mg, and 60 mg), stratified by baseline propranolol use, with at least 104 (65%, 26 participants per dose group) monotherapy participants and up to 56 (35%, 14 participants per dose group) adjunct therapy participants.

The sample size of 104 participants for the monotherapy cohort assumes a change from baseline at Day 91 in TETRAS upper limb Item 4 score for the placebo group of -1.2 points, a maximum decrease of -3.2 points from Baseline for a dose response in the 15-60mg dose groups with a standard deviation of 2.5.

Under these assumptions with a few prespecified candidate dose-response models, including linear, loglinear, quadratic, exponential, logistic, Emax, sigEmax, and beta as shown in Figure 2 (see Section 8.3.3.1 of this analysis plan for underlying parameters associated with each model), a sample size of 22 evaluable participants per group would provide 80% power for demonstrating a nonflat dose-response relationship by Multiple Comparisons Procedure - Modeling (MCP-Mod) approach, using a 1-sided type I error rate of 0.05.

Assuming a nonevaluable rate of 15% across all treatment groups, approximately 104 participants (26 per treatment group) will be randomized. Additional participants may be enrolled if the overall nonevaluable rate is higher than 20%.

The sample size for the adjunct therapy cohort is not based on statistical significance, but clinical considerations. Up to 56 adjunct therapy participants (14 per dose group) are to provide some adjunct therapy directional data on both efficacy and safety measures.

A blinded interim look of the primary and secondary endpoint data may be conducted to evaluate the sample size assumptions. Additional participants may be randomized if the

variances are larger than the assumptions above. However, no more than 200 participants, including adjunct therapy participants, will be randomized.

Figure 2: Prespecified Dose Response Models

5.3. Randomization

This is a randomized, double-blind, placebo-controlled study. Participants will be randomized in a 1:1:1:1 ratio to treatment groups (15 mg, 30 mg, 60 mg SAGE-324, or placebo), stratified by baseline propranolol use. Randomization schedules will be generated by an independent statistician, and randomization to treatment group according to the randomization schedule will be performed centrally via an interactive response technology system.

5.4. Blinding and Unblinding

This is a randomized, double-blind, placebo-controlled study. Participants, site staff, and the study team will be blinded to treatment allocation during the study. The randomization

schedules will be kept strictly confidential, accessible only to authorized personnel until the time of unblinding. The blinding of the study will be broken after the database has been locked.

During the study, the blind is to be broken only when the safety of a participant is at risk and the treatment plan is dependent on the study treatment received. Unless a participant is at immediate risk, the investigator should make diligent attempts to contact Sage prior to unblinding the study treatment administered to a participant. If the unblinding occurs without Sage's knowledge, the investigator must notify Sage within 24 hours of breaking the blind.

In all cases where the IP allocation for a participant is unblinded, pertinent information (including the reason for unblinding) must be documented in the participant's records and in the IRT. At the time of withdrawal from the study/stopping participation, if possible, an EOT and/or ETV should be conducted.

6. MODIFICATIONS

6.1. Modifications from the Approved Clinical Study Protocol

Protocol Amendment 3 (Version 4.0 dated 07-Oct-2022) permitted alcohol consumption with restrictions on amount and timing with respect to scheduled study visits. The summarization and main analysis of the primary endpoint will be repeated for categories of whether alcohol historically helped tremor (see Section 8.3.3.4).

Protocol Amendment 4 (Version 5.0 dated 10-Jan-2023) included an update to eligibility criteria and statistical analyses to include participants who are receiving propranolol for the treatment of essential tremor.

- Objectives and endpoints were updated to include the monotherapy cohort (SAGE-324), adjunct therapy cohort (SAGE-324 + propranolol), and overall population.
- Sample size and power were updated to focus on required enrollment for monotherapy participants; the adjunct therapy cohort was not based on statistical significance, but clinical considerations.
- Randomization was stratified by baseline propranolol use.
- Summarization and analysis of the primary efficacy variable, secondary efficacy variables was updated to be performed for the monotherapy cohort (primary cohort), adjunct therapy cohort (for directional investigation, excluding MCP-Mod analysis), and overall.

6.2. Modifications from the Approved Statistical Analysis Plan

This is the first version of the SAP for the final analysis.

6.3. Modifications from the Approved DMC Charter

Not Applicable. Also note that no interim analysis was performed in this study.

7. ANALYSIS SETS

7.1. All Participants Set

The All Participants Set will include all participants who have given written informed consent and participated in the screening process. This analysis set will be used for all listings and disposition.

7.2. Efficacy Analysis Sets

7.2.1. Full Analysis Set

The Full Analysis Set will include all randomized participants who received any amount of IP and have a baseline and at least one post-baseline TETRAS Performance Subscale Item 4 (upper limb tremor) total score.

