7.3. Treatment Assignment

This is a randomized, double-blind, placebo-controlled study. Participants will be randomized in a 1:1:1:1 ratio to treatment groups (15 mg, 30 mg, 60 mg SAGE-324, or placebo), stratified by baseline propranolol use.

SAGE-324 or matching placebo will be administered orally once daily, to be taken before bed, with a snack if bedtime is not within 2 hours of the evening meal.

The placebo dose group will receive matching placebo from Day 1 to Day 90.

The 15-mg SAGE-324 dose group will receive 15 mg of SAGE-324 from Day 1 to Day 90.

The 30-mg SAGE-324 dose group will receive 30 mg of SAGE-324 from Day 1 to Day 90.

The 60-mg SAGE-324 dose group will receive 15 mg of SAGE-324 from Day 1 to Day 14, then 30 mg from Day 15 to Day 28, then 45 mg from Day 29 to Day 42, and then 60 mg from Day 43 to Day 90.

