13.1. Data Analysis Sets

The Randomized Set is defined as all participants who are randomized.

The Safety Set will include all participants who were administered IP.

The Full Analysis Set will include all randomized participants who received any amount of IP and have a baseline and at least one postbaseline total TETRAS Performance Subscale Item 4 upper limb tremor score.

The Per Protocol Set will include all participants in the Full Analysis Set without any major protocol deviations that could affect efficacy. The review of major protocol deviations will be completed, and the decision on whether the deviation affects efficacy will be documented before database unblinding.

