7.2.2. Per Protocol Set

The Per Protocol Set will include all participants in the Full Analysis Set without any major protocol deviations that could affect efficacy. The review of major protocol deviations will be completed and the decision on whether the deviation affects efficacy and results in removal of a participant from the Per Protocol Set will be documented before database unblinding. The Per Protocol Set will exclude full analysis set participants satisfying any of the following conditions:

- Study Drug Adherence (defined in Section 8.2.7) < 75%
- Inappropriate drug consumption (typically due to incorrect kit dispensation): if the participant consumed at any time during the study any study drug that the participant is not randomized to
- Day 91 efficacy assessment done 3 days or more after the last dose
- Essential tremor duration of less than 3 years
- Prohibited essential tremor medication during the treatment phase of the study (after completing the treatment is fine)
- Any other major protocol deviations that the protocol deviation review committee (PDRC) documents as impacting the primary efficacy analysis prior to the database lock.

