8.3.3. Analysis of Primary Efficacy Variable(s)

The efficacy analysis uses the Full Analysis Set and presents data by randomized treatment, unless specified otherwise. Summarization and analysis of the primary efficacy variable will

be performed for the monotherapy cohort (primary cohort), adjunct therapy cohort (for directional investigation, excluding MCP-Mod analysis), and overall.

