8.3.3.2. Sensitivity Analysis of Primary Endpoint

Sensitivity analysis of the primary endpoint will be performed to assess the robustness of the primary analysis results in the presence of missing data. For participants who terminate from treatment prior to the end of the analysis period due to adverse event, noncompliance with study procedures, death, physician decision, or use of a prohibited medication, missing measurements will be considered missing not at random (MNAR); for all other participants having missing measurements, missing values will be considered missing completely at random (MCAR).

For FAS monotherapy subjects having missing TETRAS Performance Subscale Item 4 (upper limb tremor) total score data at any visit, and, separately, for FAS subjects overall, all missing data (MCAR or MNAR) will be imputed via multiple imputation (50-100 iterations, depending on system run time) using treatment based regression methodology which includes baseline TETRAS Performance Subscale Item 4 (upper limb tremor) total score in the model, with minimum and maximum possible integer values of 0 to 24, respectively (example SAS code is found in Appendix C). The MMRM model, including the selected covariance structure, used for the main analysis of the primary efficacy endpoint will be repeated for each imputation, and the results combined and reported. The covariance matrices resulting from the MMRM run on each imputation will be combined into an overall covariance matrix will be passed to the MCP-Mod analysis to perform sensitivity analysis of the dose-response relationship. SAS code associated with this sensitivity analysis is noted in Appendix C.

If the sensitivity analysis yields a result/conclusion that is different from the result of the primary analysis, the nature of the discrepancy will be examined in order to clearly explain the discrepancy based on statistical principles, and the discrepancy will be discussed in the clinical study report.

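### Dosed monotherapy participants with no post-baseline Item 4 score fall outside every efficacy analysis, including the missing-data sensitivity analysis that should cover them

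*SAP*

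**What the plan says.** Protocol 13.1 and SAP 7.2.1 define the FAS in the same way. Participants must be randomised, have taken some investigational product (IP), and "have a baseline and at least one post-baseline TETRAS Performance Subscale Item 4 (upper limb tremor) total score" (SAP wording).

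The efficacy analyses all rest on that set:

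- SAP 8.3.3: "The efficacy analysis uses the Full Analysis Set and presents data by randomized treatment, unless specified otherwise".
- SAP 7.2.2: "The Per Protocol Set will include all participants in the Full Analysis Set without any major protocol deviations that could affect efficacy". This makes it a subset of the FAS.
- SAP 8.3.3.2, the missing-data sensitivity analysis, is limited in the same way: "For FAS monotherapy subjects having missing TETRAS Performance Subscale Item 4 (upper limb tremor) total score data at any visit", and separately FAS subjects overall. Within that group, "all missing data (MCAR or MNAR) will be imputed via multiple imputation", using a treatment-based regression.
- SAP 8.3.4 repeats the same analyses for the secondary endpoint.

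Protocol 13.1 also names a wider set: "The Randomized Set is defined as all participants who are randomized". No efficacy analysis uses it, and SAP section 7 does not define it.

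On early dosing, Protocol 7.3 says: "The 60-mg SAGE-324 dose group will receive 15 mg of SAGE-324 from Day 1 to Day 14". The 15-mg and 30-mg arms take their assigned dose from Day 1.

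**The concern.** FAS membership depends on something that happens after randomisation: being rated at least once on treatment or in follow-up. SAP 8.3.3.2 is meant to test whether the primary result survives missing data, and it labels data missing after termination for an adverse event as missing not at random. The FAS rule removes the earliest such participants before that test begins. The target population in the estimand (SAP 4.1.3) carries no such condition.

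This matters more if the loss is uneven. Protocol 5.1 and 5.2 introduce bedtime dosing for all arms and up-titration to 60 mg to reduce somnolence, and Protocol 7.4 allows no dose adjustment. In week 1 the highest daily dose is in the 30-mg arm, so dose-related early loss, if there is any, would be expected mainly there. That arm is an interior point of the dose-response curve and helps to decide its shape.

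**Working it through.** **1. Who is excluded.** TETRAS is rated at Screening and on Days 1, 8, 15, 29, 43, 57, 71, 91/EOT and 97 (SAP 8.3.1.1); Day 3 is a phone call (Protocol Table 2). Three cases follow.

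- Stops IP before Day 8 and attends the EOT visit: rated, so in the FAS. Protocol 8.4.1 encourages this visit. Under SAP 8.3.2, an early EOT rating no later than one day after the last dose is mapped by study day, and the Day 8 window runs from Day 1 postdose to Day 11.
- Stops IP before Day 8 and attends the follow-up visit 7 days after EOT: rated, so in the FAS.
- Withdraws before Day 8 with only an early termination visit (Protocol 8.4.2): the EOS/ETV column of Protocol Table 2 has no TETRAS, and the note to SAP Table 2 excludes TETRAS from that visit. There is no scheduled rating, so the participant is not in the FAS.

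**2. Where exclusion has an effect.** The MMRM code in SAP Appendix C keeps only records with a non-missing change. A participant with none adds nothing to the primary estimate under any set definition. The set matters only for the imputation analysis.

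**3. The plan's own figures.** Inputs from SAP 5.2: placebo change -1.2, largest change -3.2 (maximum effect 3.2 - 1.2 = 2.0), SD 2.5, one-sided alpha 0.05, 22 evaluable per group, 15% nonevaluable.

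- Inflation: 22 / (1 - 0.15) = 25.9, rounded up to 26 per group and 104 in all. This matches.
- Power: the eight candidate curves were built from the guesstimates in SAP 8.3.3.1 (assumed: linlog offset 0.6 and beta scale 72, taken as package defaults) and the maximum-contrast test was simulated (200,000 draws, 84 degrees of freedom). Power ranges from 79.4% (beta) to 86.7% (exponential). The minimum agrees with the stated 80%.

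**4. Effect at 30 mg under two of the plan's curves.**

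- Linear: 2.0 x 30/60 = 1.0.
- Emax: 80% of the maximum at 30 mg gives ED50 = 30 x 0.2/0.8 = 7.5. Scaled to 2.0 at 60 mg: 2.0 x (30/37.5) / (60/67.5) = 2.0 x 0.8/0.889 = 1.8.

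**5. Illustration.** Suppose k of 26 in the 30-mg arm leave with no rating and are put back with no drug effect. The 30-mg effect shrinks by (k/26) x effect.

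| k | k/26 | Linear (1.0) | Emax (1.8) | Minimum MCP-Mod power |
|---|---|---|---|---|
| 0 | 0 | 0 | 0 | 79.4% |
| 1 | 0.038 | 0.04 | 0.07 | 78.6% |
| 2 | 0.077 | 0.08 | 0.14 | 77.9% |
| 3 | 0.115 | 0.12 | 0.21 | 77.2% |
| 4 | 0.154 | 0.15 | 0.28 | 76.5% |

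The power column uses 22 per group and dilutes only the 30-mg mean. k is an assumption, and k = 4 would put the plan's whole 15% allowance for that arm into the first week.

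**6. Scale.** The standard error of a pairwise difference is 2.5 x sqrt(2/22) = 0.75. The largest shift in the table, 0.28, is a little over a third of that.

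**The case against.** Several points on the other side stand.

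- A reader might infer that stopping treatment before Day 8 removes a participant from the FAS. It does not: one EOT or follow-up rating keeps them in, and the protocol encourages those visits. The excluded group may be small or empty.
- A reader might infer that the loss would go unseen. SAP 8.2.1 already plans analysis-set counts by arm and stratum, a listing of those excluded from each set, and treatment-discontinuation reasons by arm. What is missing is an analysis showing what the loss does to the result.
- A reader might infer that the FAS rule biases the primary estimate and that a wider set would correct it. The MMRM would give the same answer with either set.
- A reader might take the table as the amount by which the 30-mg effect is overstated. SAP 4.1.3 adopts a hypothetical strategy where data are unavailable after discontinuation. Assigning no drug effect is a different and harsher assumption, so the table shows sensitivity to that assumption and does not measure error against the stated estimand.

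It can also be said that placebo-based imputation for someone who leaves on Day 6, beside own-arm regression for someone who leaves on Day 10, is uneven. That is fair. The distinction can be defended, because the first participant has no post-baseline score to inform the imputation, but the SAP should say so. How later adverse-event dropouts are imputed is a separate question.

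None of this answers the core point: the analysis written to test robustness to missing data leaves out the participants with the most missing data.

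**Conclusion.** The gap is real but narrow. Dosed monotherapy participants who leave with no post-baseline Item 4 total score are in no efficacy analysis, and the sensitivity analysis could include them at little cost. Uneven early loss is plausible from the week-1 dosing, but the documents give neither an early-loss rate nor tolerability figures for 30 mg, so neither its existence nor its direction is established.

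If 1 to 4 of 26 in the 30-mg arm left this way and had no drug effect, the 30-mg effect would fall by 0.04-0.15 points (linear) or 0.07-0.28 (Emax), and minimum power would move from 79.4% to between 78.6% and 76.5%. These sizes rest on the assumed k, on loss in the 30-mg arm alone, and on the plan's effect and SD assumptions. They are small beside a standard error of 0.75. The sample size calculation is not in error, and the primary analysis needs no change. This is an inexpensive improvement to the sensitivity analysis.

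**What to change.** In SAP 8.3.3.2, define the population for the monotherapy multiple imputation and its MCP-Mod step as all randomised monotherapy participants who received IP and have a baseline Item 4 score. A Day 1 score should exist for all of them, because inclusion criterion 6 (Protocol 8.1) requires one before dosing. Impute those with no post-baseline score from the placebo arm. State that this is a conservative sensitivity assumption that departs from the hypothetical strategy, and why it applies only to this group. Keep the FAS MMRM as the primary analysis. No new count table is needed, since SAP 8.2.1 already provides it.

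Cost: revised SAP wording, one population flag, and a placebo-based imputation step added to the Appendix C code. No new data are collected. The sensitivity estimate may be slightly less favourable; the primary estimate does not move.
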